### **6.2 Secondary objective**

To assess the clinical impact and risk factors related to influenza-related invasive pulmonary aspergillosis. Patients with proven or probable IPA will be compared to patients that do not meet the criteria for proven and probable IPA. Baseline characteristics and clinical data such as SAPS3, SOFA score, need for invasive ventilation and need for continuous renal replacement therapy, will be assessed to find risk factors for IPA.

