### 9.1 Data to be collected Baseline

#### characteristics

Date of ICU admission

Age

Sex

SAPS3-score on arrival to the ICU SOFA-

score on arrival to the ICU Presence of:

Liver cirrhosis (defined as Child-Pugh-score  $\geq$ A)

Heart failure (defined as ejection fraction  $<$ 40%)

Diabetes mellitus (not diet treated)

Renal failure (defined as creatinine clearance  $<$ 30 mL/min/1.73m^2)

Body Mass Index  $>$ 30 kg/m^2

Haematological malignancy

Hematopoietic stem cell transplantation

Organ transplantation

Daily smoking in the last year

Solid tumour

Neutropenia (defined as  $<$ 0,5 x10^9 neutrophils)

Chronic obstructive pulmonary disease

New lung infiltrate

Treatment with corticosteroids in the last 28 days

Treatment with corticosteroids in a dose equal to or above 15 mg/day prednisone

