## **11 STUDY ENDPOINTS**

Enrolled patients will be categorized as proven or probable IPA at discharge from the ICU to answer the primary objective of evaluating the prevalence of influenza related invasive pulmonary aspergillosis. A modified version of the Asp-ICU criteria will be used, described below 11.1, 11.2.

All recorded baseline characteristics will be compared between patients diagnosed with IPA and those that were not. The following outcome parameters will also be assessed: SOFA-score, use of mechanical ventilation, use of non-invasive ventilation, use of vasopressor, use of renal replacement therapy, ARDS-grade using the Berlin definition, median number of ICU stay, ICU mortality, and 90-day mortality after ICU admission.

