## **12 STATISTICAL ANALYSIS**

Prevalence of Proven/Probable IPA will be calculated at the 95% confidence level. Patients meeting the criteria for proven/probable IPA will be compared to the influenza positive patients who do not meet the criteria, in terms of underlying risk factors and outcome measures. Categorical variables will be assessed by Fischer exact test and  $X^2$  test, and continuous variables with t-test or Mann Whitney U test where appropriate. We will also perform multivariable analysis by binary logistic regression to detect independent risk factors for IPA. All analyses will be conducted using a threshold of 95% confidence level (P-value 0.05). ICU mortality and 90 days after admission to the ICU mortality will be compared using survival analysis.

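### Section 12 specifies no adjustment for the mortality comparison of IPA with non-IPA patients, so a crude difference could be read as the clinical impact of IPA

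*Combined protocol and SAP*

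**What the plan says.** Section 6.2 sets a secondary objective in two halves: "To assess the clinical impact and risk factors related to influenza-related invasive pulmonary aspergillosis". Section 11 lists the outcomes to be assessed, among them "ICU mortality, and 90-day mortality after ICU admission".

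Section 12 gives the analyses:

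- The group contrast: "Patients meeting the criteria for proven/probable IPA will be compared to the influenza positive patients who do not meet the criteria", covering both risk factors and outcomes. The tests named are two-group tests for categorical and continuous variables.
- Mortality: "ICU mortality and 90 days after admission to the ICU mortality will be compared using survival analysis". No model, covariate, stratification, weighting or matching is given.
- The only multivariable analysis: "We will also perform multivariable analysis by binary logistic regression to detect independent risk factors for IPA".

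Section 9.1 collects, at baseline, "SAPS3-score on arrival to the ICU", SOFA on arrival, "Treatment with corticosteroids in the last 28 days", and host factors such as "Haematological malignancy", transplantation and neutropenia. No section enters any of these into a mortality analysis.

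**The concern.** IPA status is observed, not assigned. Section 6.2 treats SAPS3, SOFA, invasive ventilation and renal replacement as candidate risk factors for IPA, and section 11 compares all recorded baseline characteristics between the groups. Several of these, such as admission severity and immunosuppression, could plausibly raise the risk of death whether or not IPA develops. A factor that raises both risks makes crude mortality higher in the IPA group even if IPA has no effect on death.

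The plan provides adjustment for the risk-factor half of the objective and none for the impact half. A logistic model for IPA cannot adjust a contrast in mortality, because death is not its outcome. At stake is how a crude excess of deaths is interpreted, in a study whose section 5.2 links its results to national guidelines. Leaving the covariates open also allows them to be chosen after the results are seen.

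**Working it through.** **The plan's own figure.** Section 7.2 gives at least 50 patients, 15% expected prevalence and a 10-point margin at 95% confidence. The simple precision formula gives n = 1.96² × 0.15 × 0.85 / 0.10² = 48.98, rounded up to 49, so the stated 50 reproduces. The plan gives no mortality rate, event count or effect size for the mortality comparison.

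**Inputs.** From section 7.2: 15% IPA, N = 50 as the minimum, and about 100 admissions per season. Assumed: 20% overall mortality; one binary factor with prevalence p of 0.3-0.4; risk ratio r for IPA and s for death, each 1.5-3; no effect of IPA on death.

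**Spurious ratio.**

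- IPA risk with the factor: a₁ = 0.15r / (1 + p(r − 1))
- Factor prevalence in IPA patients: q₁ = pr / (1 + p(r − 1))
- Factor prevalence in non-IPA patients: q₀ = p(1 − a₁) / 0.85
- Mortality without the factor: m₀ = 0.20 / (1 + p(s − 1))
- Mortality in each group: m₀(1 + q(s − 1))

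Worked case, p = 0.3 and r = s = 3: a₁ = 0.45/1.6 = 0.281; q₁ = 0.9/1.6 = 0.5625; q₀ = 0.3 × 0.719/0.85 = 0.254; m₀ = 0.20/1.6 = 0.125. Mortality is 0.125 × 2.125 = 26.6% in IPA and 0.125 × 1.507 = 18.8% in non-IPA patients, a ratio of 1.41.

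| p | r = s | IPA | non-IPA | Ratio |
|---|---|---|---|---|
| 0.3 | 1.5 | 20.8% | 19.9% | 1.05 |
| 0.3 | 2 | 22.5% | 19.6% | 1.15 |
| 0.4 | 3 | 25.9% | 19.0% | 1.37 |
| 0.3 | 3 | 26.6% | 18.8% | 1.41 |

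As a cross-check, a different set-up fixes the factor's prevalence at 30% in non-IPA and 40-70% in IPA patients, with a death risk ratio of 1.5-2.5. It gives 1.04 to 1.41.

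**Sampling error.** SE of the log risk ratio = √(1/d₁ − 1/n₁ + 1/d₀ − 1/n₀).

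- N = 50, 20% mortality: 7.5 IPA patients with 1.5 deaths and 42.5 others with 8.5 deaths. SE = √(0.667 − 0.133 + 0.118 − 0.024) = 0.79. The 95% interval spans a factor of exp(1.96 × 0.79) ≈ 4.7 either way. The largest illustrated bias, ln 1.41 = 0.34, is about 0.4 SE.
- N = 100, assumed 40% mortality: 15 IPA patients with 6 deaths and 85 others with 34 deaths. SE = √(0.167 − 0.067 + 0.029 − 0.012) = 0.34. The same bias is about 1 SE.

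**Room to adjust.** If 90-day mortality is 20-40% (assumed), N = 50 gives 10-20 deaths and N = 100 gives 20-40. A model with IPA and SAPS3 has two terms: 5-10 deaths per term at N = 50 and 10-20 at N = 100. A third term lowers this to about 3-7 and 7-13.

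**The case against.** The strongest reply is that the plan is silent, not wrong: survival analysis covers an adjusted Cox model as well as crude curves. That is correct. A reader might infer that the plan commits to an unadjusted comparison, but it does not say so. What stands is that a crude comparison would meet the plan in full, and that no covariates are fixed in advance.

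Three other strong readings also go beyond the text:

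- *The plan expects the groups to differ.* Section 6.2 describes a search for risk factors, not an expectation, and section 5.1 says most influenza patients in ICU lack the classical ones. The documents give neither the frequency of any confounder nor its effect on death.
- *Mortality is the main measure of clinical impact.* Section 11 lists mortality with SOFA, ventilation, vasopressors, renal replacement, ARDS grade and ICU stay, and ranks none of them.
- *Deaths will be attributed to IPA.* The plan speaks of assessing and comparing. A causal reading is a risk, not a stated intention.

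It can also be said that imprecision limits this comparison more than confounding of the illustrated size. Near 50 patients that is right, and it lowers the priority. It does not justify leaving the covariates open: with few deaths, a short list fixed beforehand matters more.

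Finally, adjustment for one score would not deal with host factors or with the timing of the IPA diagnosis. Both limits stand and have to be stated with the result.

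**Conclusion.** The point holds as a gap in specification. Nothing in the plan adjusts ICU or 90-day mortality, the groups are not randomised, and the plan already collects a suitable severity score. A crude difference could be read as the impact of IPA when part of it reflects prior illness or treatment.

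Neither the direction nor the size of the confounding can be established from the documents. The range of about 1.05 to 1.41 rests on assumed values for everything except the 15% prevalence, and on a single factor that raises both risks. Several such factors together could give more. The documents do not support the conclusion that the clinical-impact question goes unanswered: other impact outcomes are listed, and an adjusted analysis is not ruled out.

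This is a cheap improvement to a secondary objective. The prevalence estimate and the target of 50 are unaffected.

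**What to change.** In section 12, pre-specify:

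1. For 90-day mortality, a Cox model of IPA status adjusted for SAPS3 on ICU arrival. For ICU death, a penalised logistic model with the same terms.
2. A second, sensitivity model that adds corticosteroid treatment in the last 28 days.
3. Adjusters restricted to values from ICU arrival or earlier. Daily SOFA, organ support and corticosteroids recorded after enrolment may follow IPA and should not be used as baseline values.
4. Crude and adjusted estimates side by side with 95% intervals, both described as associations.

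State two limits with the result. Residual confounding by host factors remains, because neither model contains them. A timing bias also remains: section 11 classifies IPA at ICU discharge, while section 9.1 follows survival from ICU admission, so a patient who dies early has less opportunity to be classified as IPA. Covariate adjustment does not remove this.

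The cost is a few lines of SAP text and two short models per mortality endpoint on data already collected. The downside is a wider interval and room for only one or two adjusters near 50 patients, where about 10-20 deaths are expected if mortality is 20-40%.

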## **13 FUNDING**

The study has received financial support from:

- Regionala forskningsrådet i Uppsala-Örebroregionen
- Centrum för klinisk forskning, Västerås

#### **14 INSURANCE**

Svenska patientförsäkringen

#### **15 PUBLICATION**

The study will be published in a peer-reviewed medical journal. All study site investigators will be awarded recognition as collaborator in the manuscript. To gain full authorship the site must include at least 10 participants and the investigator contribute according to the Vancouver definitions.

